## 7.2 Neurocognitive Testing (Research)

- 7.2.1 **Certification:** All members of the study team that will be administering the neurocognitive tests will need to be certified. Previous certification in the prior two years is acceptable. If necessary, refresher certification will be provided to any study personnel that are uncertain about test administration even if they have undergone certification within the past two years. This certification process will be under the direction of [name] [contact]).
- 7.2.2 **Timing of Assessments:** Evaluations will be performed  $\leq$  21 days before starting chemo radiation (may complete as late as day 1 of RT/TMZ),  $\leq$  7 days prior to initiation of cycle 1 of adjuvant TMZ, and every 6 months ( $\pm$  1 month) thereafter for approximately 2 years after RT completion. (See Table in section 7.1) In case of disease progression within 2 years from cycle 1, patients will be re-tested for the final time only if previous assessment was  $>$  3 months from date of progression.
- 7.2.3 **Tests to be administered:** Hopkins Verbal Learning Test – Revised (HVLT-R), Controlled Oral Word Association test from the Multilingual Aphasia Examination (COWA), Trail Making Test A and B, and Recall and Recognition of Word List encoded from the HVLT-R.

- 7.3 **Quality-of-Life (QOL) Testing (Research):** These questionnaires have been validated in the brain tumor population and used in other large, prospective studies for this patient population, providing a good potential comparison group for patients on this study. Subjects can opt out of this assessment if they so choose.
  - 7.3.1 **Timing of Assessments:** Evaluations will be performed  $\leq$  21 days before starting chemo radiation (may complete as late as day 1 of RT/TMZ),  $\leq$  7 days prior to initiation of cycle 1 of adjuvant TMZ, and every 6 months ( $\pm$  1 month) thereafter for

approximately 2 years after RT completion. (See Table in section 7.1) In case of disease progression within 2 years from cycle 1, patients will be re-tested for the final time only if previous assessment was > 3 months from date of progression.

**7.3.2 QOL Questionnaires:** EORTC Quality of Life Questionnaire-Core 30/Brain Cancer Module-20 (EORTCQLQ30/BN20); M. D. Anderson Symptom Inventory Brain Tumor Module (MDASI-BT)

## 8.0 TREATMENT PLAN

### 8.1 Radiation Therapy

**8.1.1 Timing of Radiotherapy:** RT must begin  $\leq$  50 days from resection. Daily oral temozolomide will start together with the first day of radiation. RT may start on M-Th. Temozolomide is given every day during course RT (M-Su) up to a total of 42 doses (may halt as early as 40 doses if RT is completed prior to 42 dose course).

**8.1.2 Certification:** IMRT or VMAT technique will be used for all cases. To utilize IMRT or VMAT on this study, proper credentials are required. Previous certification by the Radiological Physics Center (RPC) for use of IMRT or VMAT on another protocol is acceptable.

**8.1.3 Radiation Energy:** Minimum photon energy is 6 MV with IMRT or VMAT plans designed and verified by simulation. Minimum SSD or SAD is 80 cm.

#### 8.1.4 Target Volume Definitions

**8.1.4.1 ICRU Definitions:** ICRU terminology defines the gross tumor volume (GTV) and clinical tumor volume (CTV) as the extent of gross and microscopic disease, respectively. The planning target volume (PTV) is geometrically, not anatomically, defined and is an expansion of the CTV intended to account for uncertainty in patient positioning.

**8.1.4.2 GTV1:** This volume encompasses the edema and T2 hyper-intensity surrounding the main tumor mass as estimated from the T2-weighted or FLAIR postoperative MRI scan. By definition, this volume will also include all of GTV2 and GTV3.

**8.1.4.3 GTV2:** This volume encompasses the post-operative resection cavity (as seen on both T1 post-contrast and T2 sequences) plus any contrast enhancing volume or mass that is considered likely to represent residual enhancing tumor. Fusion of the pre-operative T1-weighted, contrast enhanced MRI is also encouraged to allow comparison with RT planning MRI to ensure inclusion of the pre-operative localized contrast-enhancement or mass within the GTV2. GTV2 may be modified to account for anatomic changes post-operatively to respect the anatomic structures within which the tumor was initially bound. For example, if a large tumor with mass effect has been resected, anatomically distant brain parenchyma may post-operatively be within the fusion-generated GTV2. GTV2 may be modified to exclude geographically distant brain parenchyma in this situation. By definition, this volume will also include all of GTV3.

**8.1.4.4 GTV3:** This volume will encompass the volume of Cho/NAA ratio  $\geq 2x$  contralateral normal brain from the pre-RT sMRI scan plus any T1 contrast enhancing residual seen on the post-operative and pre-RT diagnostic brain MRIs. This can be modified at discretion of treating physician(s) with consultation with other investigator(s), as needed.

**8.1.4.5 CTV1:** This volume includes GTV1 plus a 5 mm margin (at discretion of treating radiation oncologist). CTV1 may be anatomically confined, for

example, to within the calvarium. However, high grade gliomas can invade most intracranial structures and should not be confined by the tentorium or an arbitrary midline. This expansion can be excluded from the brainstem and optic chiasm/nerves at the treating physician's discretion if there is not felt to be risk of extension into these regions. By definition, this volume will completely encompass CTV2 and CTV3

**8.1.4.6 CTV2:** This volume includes GTV2 plus a 5 mm margin cropped to be completely encompassed by CTV1. By definition, this volume will also completely encompass CTV3.

**8.1.4.7 CTV3:** This volume includes GTV3 with no margin cropped to be completely encompassed by CTV1 and CTV2.

**8.1.4.8 PTV1, PTV2 and PTV3:** These volumes are uniform 3 mm expansions of CTV1, CTV2 and CTV3, respectively, to account for set-up uncertainty. It is not confined anatomically, with the exception of cases that would otherwise exceed normal tissue tolerance (see below for normal tissue dose constraints).

**8.1.5 Prescription Isodose:** The prescription isodose surface (100% dose curve) shall encompass a minimum of 95% of the PTV. In addition, the entire PTV shall be encompassed by the 95% isodose surface. The dose uniformity guidelines below must be met for all PTVs.

**8.1.6 Tissue Heterogeneity:** Calculations to take into account the effect of tissue heterogeneities are required.

#### **8.1.7 Target Dose**

**8.1.7.1 Prescription dose for IMRT or VMAT techniques:** Patients will be treated with a simultaneous in-field boost plan. PTV1 will receive 5010 cGy in 30 fractions of 167 cGy per day. PTV2 will simultaneously receive 6000 cGy in 30 fractions of 200 cGy per day. PTV3 will simultaneously receive 7500 cGy in 30 fractions of 250 cGy per day.

**8.1.8 Dose Uniformity:** The entire PTV shall be encompassed within the 95% isodose surface as evaluated by dose volume histogram. Does plan should try to achieve 99% of PTVs receive at least 95% of prescription dose unless coverage needs to be compromised to meet OAR constraints. In addition, no part of PTV3 shall receive more than 110% of the prescription dose (8250 cGy) and  $\leq 10\%$  of PTV3 shall receive more 105% of the prescription dose (7875 cGy).

**8.1.9 Time Considerations:** Patients will receive one treatment per day, five days per week. All fields will be treated each day. At least two fractions must be given during the first week of treatment.

**8.1.10 Simulation:** A conventional CT or MRI simulator will be used for patient simulation. The patient shall be treated in the supine position with a head-holding device that is transparent to x-rays (thermoplast masks, bite-block, etc.) to ensure adequate immobilization and reproducible daily setup of the treatment position.

**8.1.11 Organs at Risk (OARs):** When possible, without shielding GTV/CTV/PTV, the listed OARs should not receive more than the following doses:

brainstem  $\leq 6000$  cGy (95% of volume  $\leq 5400$  cGy)

optic nerves and optic chiasm  $\leq 5500$  cGy (99% of volume  $\leq 5400$  cGy)

retina  $\leq 4000$  cGy

cervical spinal cord  $\leq 5000$  cGy

lens  $\leq$  500 cGy

No more than 1% or 1 cc of unspecified tissue outside of the PTV should receive  $>$  110% of the prescribed dose. Planning organ at risk volumes (PRVs) are recommended such that the spinal cord should have 3-dimensional expansion by 5 mm while the optic nerves, optic chiasm, and brainstem should have a 3-dimensional expansion by at least 1 mm. The dose constraints to the PRVs will be the same as for their respective OARs as outlined above. Higher priority OARs (higher priority than PTV coverage) include: brainstem, cervical spinal cord, optic nerves and optic chiasm as defined above. In these cases, PTV coverage will be compromised to keep OARs dosing within the above constraints. Lower priority OARs (lower priority than PTV coverage) include: parotids (entire volume)  $\leq$  10 Gy; oral cavity/lips/nasal cavity mean dose  $\leq$  20 Gy and  $<$  1% receiving  $>$  40 Gy; inner/middle ear mean dose  $\leq$  30 Gy and  $<$  1% receiving  $>$  50 Gy; and lens/retina as defined above. For example (for the lower priority OARs), typically 100% of the parotids should receive  $\leq$  10 Gy, but tumor coverage is of higher priority leading to cases where this dose may exceed 10 Gy.

**8.1.12 IMRT or VMAT Plan Verification:** The monitor units used for the IMRT or VMAT plan must be independently checked prior to the patient's first treatment. Measurements in a QA phantom can suffice for a check as long as the plan's fluence distribution can be re-computed for a phantom geometry.

**8.1.14 Verification of treatment set-up:** Orthogonal pair of reference films is sufficient for the initial and subsequent ports. While setup checks using orthogonal pairs are required at least weekly, use of daily kV OBI equipment to check and reset the isocenter is encouraged.

## 8.2 Treatment schedule

### Concurrent RT/TMZ (~42 days + 4-6 week break)

Agent	Dose level	Route	Schedule
RT	75 Gy	Ext. beam	1x/day on M-F for 30 txs, may start M-Th
TMZ	75 mg/m 	Oral	1x/day, 7 days/week on M-Su during RT 
4-5 week treatment break after completion of RT 			

### Adjuvant TMZ, Cycles 1-12 (28 days) at the discretion of the treating physician (Standard)

 TMZ will start with 1st RT treatment. If RT is extended due to holidays or unplanned breaks, up to 7 additional doses of TMZ can be given (up to 49 days). While a typical TMZ course will involve 42 days, the last dose will be on the last day of RT. This may result in as few as 40 days of TMZ if the first day of RT falls on a Monday and there are no breaks resulting in completion of RT on Friday of the 6th week of therapy.

 Rest period may extend longer depending on dose limiting toxicity.

**8.2.1 Administration of temozolomide (Standard care):** TMZ dosing will be based on actual body weight. The smallest TMZ capsules are 5 mg. Therefore, patient doses of TMZ will be rounded to the nearest interval of 5 mg. TMZ capsules should be taken preferably in the morning for the concurrent RT/TMZ course with up to 200 mL of water on an empty stomach one hour before or two hours after food. Evening/night dosing of TMZ right before bedtime can be used during adjuvant TMZ therapy (cycles 1-12). If possible, TMZ should be taken 2-3 hours before RT but the timing of the dose is left to the discretion of the treating physician. Since TMZ may cause nausea, an

appropriate anti-emetic (e.g., 1 mg dose of granisetron or 4-8 mg of ondansetron) should be given once a day before the TMZ. On days when patients do not have radiation, they should continue to take temozolomide in the morning on an empty stomach at approximately the same time as radiation days.

**8.2.2 *Pneumocystis jirovecii pneumonia [PJP (PCP)] prophylaxis:*** Since low dose TMZ is immunosuppressive and associated with an increased risk of PJP, all subjects must receive prophylaxis during RT with concomitant TMZ. Prophylaxis must be continued for at least two weeks after the completion of RT. The choice of prophylactic medications will be left to the discretion of the treating physician. Options include atovaquone and dapsone. Based on NABTC experience, trimethoprim/sulfamethoxazole (Bactrim) appears to contribute to myelosuppression in patients on chemotherapy. Thus, this agent is not preferred. It may be used in patients who cannot tolerate other options listed above, although the final decision will be left to the discretion of the treating physician. The decision to continue PJP prophylaxis beyond the time points noted is left to the discretion of the treating physician. Subjects who continue to demonstrate lymphopenia after the continuous daily dosing of TMZ has been discontinued should be considered for ongoing prophylaxis.

**8.2.3 *Treating physician:*** Subjects will be treated as outpatients. All treatments are prescribed/given by study physicians. During RT, subjects will be evaluated on a weekly basis. During the adjuvant TMZ phase, subjects will be evaluated on a q28 day basis.

## **9.0 DOSAGE MODIFICATION BASED ON ADVERSE EVENTS**

Follow modifications based information given below until individual treatment tolerance can be ascertained. If multiple adverse events are seen, administer dose based on greatest reduction required for any single adverse event observed. If an adverse event is not covered below, doses may be reduced or held at the discretion of the treating physician for the subject's safety. Dose adjustments for hematological adverse event are based on the blood counts obtained in preparation for the day of treatment.

**9.1 *Radiation therapy:*** While interruption due to acute radiation adverse events is unlikely given the type of radiation planned, individual reasons, such as major worsening of neurological or mental status or any other medical condition may preclude the continuation of radiotherapy. Resuming RT in this setting will be at the discretion of the treating physician. For example, cranial irradiation can be withheld for CNS adverse events or toxicity  $\geq$  grade 3 attributable to radiotherapy. The overall time of interruption and overall time of radiotherapy must be recorded. If radiotherapy is interrupted, actions regarding dosing on concomitant temozolomide are described below:

- If administration of TMZ is interrupted, RT will proceed normally and no catch up days of TMZ will be given after end of RT.
- If RT extends beyond 42 days because of delays, TMZ may be extended to a maximum of 49 days (at discretion of treating physician). If RT is still not completed, additional TMZ beyond 49 days is not permitted.
- If RT is stopped for an adverse event felt clearly related to radiation and not TMZ, concomitant TMZ should be continued as per protocol unless PD occurs.

**9.2 *Concomitant treatment:*** If the attribution of the adverse event can be clearly linked to TMZ, these dose modifications should be followed.

**9.2.1 *Dose modification criteria for TMZ during RT (chemoradiation phase):*** Concurrent TMZ dose for cycle 1 is 75 mg/m^2 given every day (including weekends) over the RT course (up to a maximum of 49 days). Maximum dose reduction is 50% of the starting dose. If significant toxicity is still experienced at 50% of the starting dose, TMZ will be

discontinued.

Use Common Terminology Criteria for Adverse Events (CTCAE) v4.0 unless otherwise specified		
Dose modification criteria for TMZ (during concurrent RT/TMZ phase)		
CTCAE Category	Adverse Event	Dosage Change
Blood/bone marrow	Grade 2 - ANC<1500-1000 or PLTS<100,000-50,000	Continue RT but omit TMZ until ANC≥1500 and PLTS≥100,000, ↓TMZ dose by 15%.
	Grade 3 - ANC<1000-500 or PLTS<50,000-25,000	Continue RT but omit TMZ until ANC≥1500 and PLTS≥100,000, ↓TMZ dose by 25%.
	Grade 4 - ANC<500 or PLTS<25,000	Hold RT and TMZ. Resume RT when ANC ≥500 & PLTS≥25,000 and TMZ when ANC≥ 1500 & PLTS≥100,000, ↓TMZ dose by 50%.
Gastrointestinal	Grade 2 - Nausea/vomiting on optimal anti-emetics	TMZ may be held until recovery to grade 0-1 at physician's discretion.
	Grade 3 - Nausea/vomiting on optimal anti-emetics	Omit TMZ until grade 0-2 (or ≤1 grade of baseline), ↓TMZ dose by 25%.
	Grade 4 - Nausea/vomiting on optimal anti-emetics	Omit TMZ until grade 0-2 (or ≤1 grade of baseline), ↓TMZ dose by 50%.
Non-hematologic Other	Grade 2	TMZ may be held until recovery to grade 0-1, ↓TMZ dose by 15% at physician's discretion.
	Grade 3	Omit TMZ until grade 0-2 (or ≤1 grade of starting value for pre-existing abnormalities), ↓TMZ dose by 25%.
	Grade 4	Omit TMZ until grade 0-2 (or ≤1 grade of starting value for pre-existing abnormalities), ↓TMZ dose by 50%.
Development of alopecia does not require dose modification		

**9.3 Adjuvant treatment:** If the attribution of the adverse event can be clearly linked to TMZ, these dose modifications should be followed.

During adjuvant therapy only, patients who require resection for radiation necrosis without evidence of recurrent tumor may continue to receive protocol therapy as long as they are not off study drug for >6 consecutive weeks.

**9.3.1 Dose modification criteria for adjuvant TMZ after RT (cycles 1-12):** Adjuvant TMZ dose for cycle 1 is 150 mg/m^2 given days 1-5 of 28 day cycle. This dose is used even if TMZ dose reductions or treatment delays were necessary during concurrent RT/TMZ

as long as other criteria at time of starting cycle 1 do not preclude beginning adjuvant TMZ therapy. If tolerated, subsequent cycles will increase dose to 200 mg/m^2 given days 1-5 of 28 day cycles. Maximum dose reduction is 50% of the starting dose (75 mg/m^2 if dose reduction required after cycle 1 or 100 mg/m^2 if dose reduction required after cycle 2 or later). If significant toxicity is still experienced at 50% of the starting dose, TMZ will be discontinued.

Use Common Terminology Criteria for Adverse Events (CTCAE) v4.0 unless otherwise specified		
Dose modification criteria for TMZ at time of retreatment		
CTCAE Category	Adverse Event	Dosage Change
Blood/bone marrow	ANC<1500 or PLTS<100,000	Hold TMZ until ANC≥1500 and PLTS≥100,000, ↓TMZ dose based on nadirs (see table below based on interim AEs). If no recovery for > 4 weeks then discontinue TMZ.
Non-hematologic Other	Grade 3/4	Hold TMZ until recovery to grade 0-1, ↓TMZ based on interim AEs (see table below). If no recovery for > 4 weeks then discontinue TMZ.

Use Common Terminology Criteria for Adverse Events (CTCAE) v4.0 unless otherwise specified		
Dose modification criteria for TMZ based on interim adverse events		
CTCAE Category	Adverse Event	Dosage Change
Blood/bone marrow	Grade 3 - ANC<1000-500 or PLTS<50,000-25,000	↓TMZ dose by 25%. (Hold TMZ based on above table's criteria)
	Grade 4 - ANC<500 or PLTS<25,000	↓TMZ dose by 50%. (Hold TMZ based on above table's criteria)
Gastrointestinal	Grade 3 - Nausea/vomiting on optimal anti-emetics	↓TMZ dose by 25%.
	Grade 4 - Nausea/vomiting on optimal anti-emetics	↓TMZ dose by 50%.
Non-hematologic Other	Grade 3	↓TMZ dose by 25%. (Hold TMZ based on above table's criteria)
	Grade 4	↓TMZ dose by 50%. (Hold TMZ based on above table's criteria)

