Based on this study, the recommended starting dose of temozolomide for Phase II trials was 150 mg/m^2/day, orally, once a day for 5 days (total dose 750 mg/m^2) for the first cycle with subsequent dose escalation to 200 mg/m^2/day, once a day for 5 days (total dose 1000 mg/m^2) in the absence of myelotoxicity. The CRC subsequently conducted three Phase II trials of temozolomide in patients with documented progression who had either high-grade glioma, advanced malignant melanoma, or low-grade non-Hodgkin's lymphoma (Investigator's Brochure -Temozolomide. Schering Plough) [24]. Activity in these tumor types was reported in all three studies.

**5.1.14.2 Temozolomide for Recurrent Malignant Gliomas:** A randomized trial was conducted to compare the efficacy of temozolomide with procarbazine in patients with GBM at first relapse [25]. Patients were randomized to temozolomide administered orally once daily for 5 days at a starting dose of either 200 mg/m^2/day (no prior chemotherapy) or 150 mg/m^2/day (prior chemotherapy) every 28 days, or procarbazine 150 mg/m^2/day for 28 days every 56 days. Temozolomide performed better than procarbazine in terms of progression free survival (PFS), overall survival and objective response to treatment, although the differences were modest. The 6-months progression free survival (6M-PFS) was 21% in the temozolomide group compared to 8% in the procarbazine group (p=0.008). In comparison, the 6M-PFS for GBM patients in 8 negative phase II trials from MD Anderson Cancer Center was only 15% (Wong et al, 1999). Median PFS was 2.89 months with temozolomide compared to 1.97 months with procarbazine. The median overall survival for the intent-to-treat population of temozolomide recipients with GBM (7.34 months) was longer than for procarbazine recipients (5.82 months). 5.4% of TMZ patients and 5.3% of procarbazine patients had a PR, while 40.2% of temozolomide patients and 27.4% of procarbazine patients had SD. The overall response rate (PR + SD) was 45.6% in the temozolomide group and 32.7% in the procarbazine group [25]. The most common grade 3 or 4 toxicities in the temozolomide group were headache (10%), thrombocytopenia (7%), neutropenia (4%), fatigue (3%), vomiting (4%) and nausea (4%). Quality of life was significantly better in the temozolomide group.

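### Section 9.3.1 sets the adjuvant temozolomide dose floor by cycle number, so a patient never escalated from 150 mg/m² is stopped at 100 mg/m² where the 50% limit gives 75 mg/m²

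*Combined protocol and SAP*

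**What the plan says.** All of the rules at issue are in section 9.3.1 of the combined protocol and SAP.

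- **Dose.** Adjuvant TMZ begins at 150 mg/m² on days 1 to 5 of a 28-day cycle. Escalation is conditional: "If tolerated, subsequent cycles will increase dose to 200" mg/m².
- **Limit.** "Maximum dose reduction is 50% of the starting dose". A parenthesis turns this into two figures: 75 mg/m² for a reduction needed after cycle 1, and 100 mg/m² "if dose reduction required after cycle 2 or later".
- **Discontinuation.** "If significant toxicity is still experienced at 50% of the starting dose, TMZ will be discontinued".
- **Size of the cut.** In the interim adverse event table, the grade 4 haematological row and the grade 4 row for other non-haematological events carry the same instruction: "TMZ dose by 50%. (Hold TMZ based on above table's criteria". Grade 3 events call for a 25% cut.
- **Hold.** The retreatment table withholds TMZ until ANC is at least 1,500 and platelets at least 100,000, or until other grade 3/4 events return to grade 0-1. It stops TMZ if recovery takes more than four weeks.

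No clause covers a patient who reaches cycle 2 or later without having been escalated.

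**The concern.** The floor changes with cycle number, but the dose it is meant to halve changes with tolerance. The two move together only on the planned path from 150 to 200 mg/m². Because escalation is conditional, the protocol itself expects that some patients may stay at 150 mg/m², and for them 100 mg/m² is not half of anything they received.

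Two things are at stake. A patient who has just had a grade 4 event could resume TMZ at a higher dose than the table row and the 50% limit call for. And because discontinuation depends on the same 50% level, investigators at the three sites could differ on when such a patient must stop.

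**Working it through.** **Inputs** (all from 9.3.1): first adjuvant dose 150 mg/m²; conditional dose 200 mg/m²; maximum reduction 50%; grade 3 cut 25%; grade 4 cut 50%; five dosing days per cycle.

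**Step 1: reproduce the stated floors.** Floor = 0.5 × dose.
- 0.5 × 150 = 75 mg/m²
- 0.5 × 200 = 100 mg/m²

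Both figures reproduce. The second shows that the parenthesis takes 200 mg/m² as the dose to be halved from cycle 2 onwards.

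**Step 2: patient escalated to 200 mg/m².**
- Grade 3: 200 × 0.75 = 150
- Grade 4: 200 × 0.5 = 100

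Neither falls below 100, so there is no conflict.

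**Step 3: patient never escalated, first reduction after cycle 2 or later.**
- Grade 3: 150 × 0.75 = 112.5, above 100, so no conflict.
- Grade 4: 150 × 0.5 = 75, which is also the 50% limit. The literal floor allows no less than 100.

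**Step 4: size of the conflict in the grade 4 case.**

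| | 50% limit and grade 4 row | Literal floor |
|---|---|---|
| Daily dose | 75 mg/m² | 100 mg/m² |
| Cut from 150 | 1 − 75/150 = 50% | 1 − 100/150 = 33% |
| Five-day cycle total | 5 × 75 = 375 mg/m² | 5 × 100 = 500 mg/m² |

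The literal dose is 100/75 = 1.33 times the intended one.

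**Step 5: does rounding absorb it?** Section 8.2.1 says "patient doses of TMZ will be rounded to the nearest interval of 5 mg". The gap is 100 − 75 = 25 mg/m² per day. Assuming a body surface of 1.6 to 2.0 m² (not given in the documents), that is 25 × 1.6 = 40 mg to 25 × 2.0 = 50 mg per day. Rounding does not remove it.

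**Step 6: the discontinuation rule.** At 100 mg/m² this patient is on 100/150 = 67% of the dose received. If the 50% level means 75, the patient has not reached it, so toxicity at 100 does not trigger discontinuation, yet the floor forbids a further cut. If the 50% level means the stated 100, discontinuation is triggered. The text does not say which applies.

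**The case against.** The strongest reply is that the 50% limit is the operative rule and the parenthesis merely illustrates it for the planned path, where it is right. On that reading a patient at 150 mg/m² goes to 75, in line with the grade 4 row. That is very probably the intent, but the parenthesis is worded as a rule by cycle number and has no exception. The discretion given in section 9.0 does not settle it, because it covers only adverse events that the section does not address, and grade 4 events are addressed.

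A second reply is that no dose is given during the toxicity, since TMZ is held until recovery. This stands, and it limits the severity. It does not settle the dose at which TMZ resumes.

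A reader might go further in three ways that the documents do not support.

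- **Patients already reduced after cycle 1.** It is tempting to say that a later event moves them to the 100 mg/m² floor, or even above their current dose. The parenthesis turns on when the reduction was required, so these patients can naturally be read as staying under the 75 mg/m² floor. A limit on reductions never orders an increase.
- **A conflict over radiotherapy.** The first bullet of 9.1 says "If administration of TMZ is interrupted, RT will proceed normally", while the grade 4 haematological row in 9.2.1 holds both treatments. That row is explicit and more specific, agrees with the bullet for grades 2 and 3, and lets RT resume before TMZ. The 9.1 lead paragraph also allows RT to stop for medical reasons. The row governs, and all that is missing is a cross-reference.
- **An effect on the trial's results.** The safety criterion in 14.1.2 and the stopping rule in 14.4 count events at least possibly attributable to RT. Neither uses the TMZ dose floor.

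**Conclusion.** The floor in 9.3.1 is wrong as written for one group: patients never escalated from 150 mg/m² whose first reduction is for a grade 4 event after cycle 2 or later. For them the literal floor exceeds the 50% limit by 25 mg/m² per day (125 mg/m² per cycle, from 500 − 375), and the discontinuation level becomes unclear. The usual path from 150 to 200 mg/m², a reduction after cycle 1, and a single grade 3 cut from 150 mg/m² are all consistent.

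Severity is minor. The conclusion rests on reading the parenthesis literally, which a clinician may well not do. The documents give no figure from which to compute how often the case would arise. No endpoint, sample size or other statistical figure changes.

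**What to change.** In 9.3.1, replace the cycle-based parenthesis with a floor of 50% of the full adjuvant dose the patient reached: 75 mg/m² if never escalated, 100 mg/m² if escalated to 200 mg/m². Refer to the same level in the discontinuation sentence.

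Optionally, add to the first bullet of 9.1 a cross-reference to the grade 4 RT hold in 9.2.1.

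The cost is one wording amendment with IRB review at the three sites, which can go with the next planned amendment. It adds no visits, tests or patients.
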